Information in the YEF archive can only be used by approved researchers to explore whether Redthread's programme, and other programmes funded by YEF, had an impact over a longer period of time. Using the unique Pupil Matching Reference numbers added to the data by the DfE, it will be possible to link the records held in the YEF archive to other public datasets such as education and criminal justice datasets. This will help approved researchers to find out the long-term impact of the projects funded by YEF because they'll be able to see, for example, whether being part of a project reduces a child's likelihood of being excluded from school or becoming involved in criminal activity.

Data Management Plan

Assessment and use of existing data and creating new data

We will analyse existing routinely collected hospital data and may produce new quantitative and qualitative data alongside the more sensitive individual level data. Ethics approvals will be obtained from the UoB and the NHS REC and HRA where needed that will set out the usage, storage and governance of data. The research team will respect any conditions of usage set forward by the data owners and the informed consent sheets will set out how data that is collected will be used.

For interviews, when prior consent is received, all interviews will be digitally audio recorded. The recorded data will be saved on password-protected and encrypted computers of the research co-ordinator and lead for the study on UoB servers. It will be either transcribed in-house or sent electronically to a transcription agency with a confidentiality agreement in place that complies with the University's data protection policy and agreed security standards set by the funder. The transcripts will be stored on UoB servers in Word Format and will be thematically analysed by the study lead and research fellow. Where interviews are conducted remotely, a UoB teams/zoom account will be used.

Quantitative data will be stored anonymously. If any individual data is collected, participant names will be allocated a research ID number. A separate list detailing the participant name and research ID code will be stored in an encrypted file on UoB servers, separate from the rest of the project files. All UoB laptops have secure encryption which satisfies the requirements of the Data Protection Act 2018. All work involving matching using names will be on UoB encrypted machines by researchers under the PI's supervision.

All data collected will be for the specific purpose of carrying out the different phases of the feasibility studies and will be GDPR compliant.

Quality assurance of data

Data collection will be designed and reviewed to ensure integrity and quality. This will be achieved by having regular project team meetings and consulting research participants on an ongoing basis. Quality assurance of data will form a standing agenda item at all team meetings.

The project manager will have ultimate accountability and oversight for quality assurance of data; however, it will be emphasised to all team members that they have a personal responsibility to produce high quality data. In order to ensure 360-degree oversight, a selection of each lead's work will also be reviewed by the co-leads and research fellow.

Quality assurance in the merged and linked data files will be ensured via the use of clear, consistent coding that will be crosschecked by members of the research team. All provided coding will be clearly annotated so that the purpose of the code is understood by any potential user. Data will also be manually examined by more than one person, either using subsets of the data for complete examination against the original data or running frequencies of the original and newly created data, for inconsistencies and errors.

Back-up and security of data

Each study lead and research fellow will store the data on their encrypted laptop. Further data back-up will be provided by using the UoB's secure network. Backup copies of data are taken at least daily or immediately if needed.

The UoB's Information Security document can be provided upon request. The project team will be mindful of not carrying/ using devices that contain sensitive data (such as personal details of participants) in 'risky' situations e.g., all members of the project team will be made aware of the issues posed by the theft of laptops etc.

This evaluation will comply with YEF's Data Archive guidance, including the collection and long-term archiving of personal data. We have considered YEF's guidance on this and will abide by it.

Data Monitoring

A data monitoring committee (DMC) will be established, which will be independent of the study organisers, the funder and the evaluation team. The DMC will consist of two people, one of which will act as a chair. The frequency of interim analyses will depend on the judgement of the Chair of the DMC, in consultation with the steering committee. However, we anticipate that there might be one interim analysis and one final analysis.

The DMC will have unblinded access to all data and can propose the stopping of the project. The steering committee decides on the continuation of the trial and will report to the central ethics committee.

An audit is planned six months into the pilot, which will include site visits. The audit will be conducted by the DMC committee.

Personnel

Redthread team:

- Project Manager – Strategic management, liaison with all key partners, contract compliance, quality assurance
- Data and Insights Manager and Data Officer - Data Management, coordination of Programme Coordinators and liaison with hospital data teams. Expertise from external GDPR / information governance adviser and other Redthread staff for data governance and consent processes
- Programme Managers across the regions – Redthread delivery staff engagement and management - project implementation, delivery liaison with local stakeholders and adherence to local processes for the evaluation
- Programme Coordinators and Youth Work teams - project delivery at sites, and evaluation tasks.
- Head of Fundraising, Communications and Policy, Statutory Fundraising Manager, Head of Finance (and information governance lead) - funder engagement, interim project management and finance expertise.

UoB evaluation team:

For this evaluation, [name] (PM) will be the lead principal investigator, lead for the impact evaluation as well as overall Project Manager. PM will be supported by [name] [name] (JSC) who will co-lead/manage the project and lead the process evaluation.

Research support:

[name] (EE) will act as the single point of contact for UoB contributing to all phases and supporting PM and JSC in project management as needed. She is a research fellow within the Institute of Global Innovation within at the University of Birmingham.

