RT have commissioned a number of evaluations of its programme within different hospital sites. A non-peer reviewed published evaluation undertaken on the programme in St Mary's hospital in London by NPC associates^{18,26} showed promising findings, regarding reducing hospital re-attendance rates for violence (a statistically significant fall compared to a pre-programme control group). YP using the service and professionals referring into it were supportive of the programme. However, there were limitations in the study design which affected the ability to draw a causal conclusion. Similarly, an evaluation of the programme in the Queen's Medical Centre undertaken by research staff there²⁷ showed lower re-attendance rates for YP who participated in the programme (both short term crisis support and full programme of work), compared to those YP who were eligible for the programme but did not engage with it. These results were found for re-attendance for any reason and specifically for violence or assault.

Mechanism for action and key outcomes

During the co-design phase we worked with RT and their partners (Dartington Service Design Lab) to undertake a Theory of Change exercise. This work involved key stakeholders and is on-going but a draft has been produced and is described below. The work has helped clarify what the different components of the programme are and the likely channels which have outcomes for CYP. In turn, this has enabled us to clarify the short-, medium- and long-term outcomes that are expected. As a result, during our sessions, we have considered the outcomes at length in consultation with YEF and RT both separately and as part of a co-design phase. Following the co-design stage, it became clear that the primary outcome should be reattendance coded for a violence or abuse related reason to hospital within 12 months from their initial discharge date. These data are available for both intervention and controls (see detail later) and we are confident that there will be sufficient power to distinguish the two groups. The secondary outcome will be mortality by any cause one year post contact with RT (this will draw on NHS data captured in the Summary Hospital level Mortality Indicator and other data which captures mortality beyond 30 days post discharge).

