	Participation What outputs must be achieved for the short term outcomes to be achieved.	10 – 17 year olds who present at hospital having experienced or been impacted by: violence, assault or a risk of violence, whether weapon or non-weapon related, domestic or sexual violence, sexual or criminal exploitation. Referrals made by (1) hospital staff member or (2) Redthread identifying an eligible CYP when reviewing the hospital systems Planned Scale: approximately 350 CYP referred through 2022 with around 150 engaged in a longer term programme across four locations, Queen Elizabeth Hospital MTC (Birmingham), Birmingham Children’s Hospital (MTC), Queen Elizabeth Hospital LTU (Woolwich, London) and St Marys MTC (Paddington, London).
OUTCOMES	Short Term Outcomes	
 • CYP understands their diagnosis/health plan • CYP feel safer • CYP offered appropriate safeguarding support • CYP better able to attend appointments, negotiate services and access support • CYP makes own appointments/plans for specialist ongoing support • CYP experiences successful engagement with specialist services themselves • CYP has onward plan for appropriate services
	Medium Term Outcomes	
 • CYP gains greater independence (e.g. makes own plans, appointments) • Improved wellbeing, self-esteem, and confidence
	Long Term Outcomes	
 • No readmission to hospital for violence-related incidents for 12 months • Reduced risk of future harm to self and others • Reduced mortality

Underpinning Aspects

ASSUMPTIONS	EXTERNAL FACTORS
Redthread can expect to receive referrals in from partner agencies listed above.	Availability of specialist services for Redthread staff to refer on to and thresholds of these organisations.
Eligibility criteria is appropriately applied.	

Research questions and/or objectives

The overarching research question is do CYP who engage with longer term support from RT have a reduced incidence of hospital re-admission for violent injury?

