The primary objective of our proposed evaluation is to provide a robust understanding of whether the RT programme targeted at CYP experiencing violence or at risk of abuse/exploitation leads to a reduction in violence/abuse related hospital readmissions in the subsequent one-year period. We aim to undertake a 1) process/implementation evaluation to assess how well the programme is being delivered and differences between delivery locations and an 2) impact evaluation to assess whether the RT programme leads to a reduction in violence/abuse related hospital admissions and other metrics.

Success criteria and/or targets

As agreed upon with YEF and RT, this project will run in two parts. The first element relates to the successful completion of a pilot phase lasting one year. This pilot will form the first part of an efficacy study, and the data gathered may contribute to the final analyses. Set progression criteria will determine whether the pilot proceeds to the efficacy study. The agreed progression criteria include:

1. Project implementation
 - a. UoB and RT are able to make a decision on the use of the SDQ/SRDS – based on RT run pilot (August 2022) and use within the pilot study (if the tools are used).
 - b. Intervention aligns with the ToC; if there is misalignment it will be necessary to re-visit the ToC, there is in general no need to stop the intervention but rather understand why the two diverge.
 - c. 75% of actions in an agreed action plan with CYP were implemented in a collaborative process involving staff and children; if this falls below 60% (Yellow), we need to discuss why this divergence is occurring and if it reaches 50% (Red) we will refer to YEF.
 - d. Personnel records show all youth workers received adequate supervision and support; this will be reviewed by UoB team and significant divergence will be reviewed with RT and YEF.

2. Recruitment and retention
 - a. Recruitment on to the intervention and into the control group is at least 60% of planned numbers within the pilot period. Anything below that is cause for concern (Yellow) with a need to pause (Red) if the response is below 40%.
 - b. CYP referred to and accepted on to the Redthread programme meet the eligibility criteria (referral form). We would expect the majority of CYP Redthread work with to meet these criteria, anything below 90% would prompt a need to discuss with Redthread.

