 - c. Redthread are able to retain CYP in support within the intervention to work through the action plan. At least 60% of planned numbers within the pilot period should be retained for a sufficient

period to complete this work. Anything below that is cause for concern (Yellow) with a need to pause (Red) if the response is below 40%.

3. Measurement
 - a. Hospital admission records (primary outcome)
 - b. Mortality data (secondary outcome)

Follow up data collection will continue for 1 year after the intervention.

It will be important to see how easily data can be matched between NHS and RT records. Not being able to match at least 80% of referrals is cause for concern and needs to be discussed (Amber), anything below a 60% match is serious cause for concern (Red) and may require us to revisit this method of capturing data.

Some key data issues such as incomplete/missing data or noncompliance or higher attrition rates than expected need to be considered. A certain level of missing data can be handled using statistical techniques, but quarterly audits should prevent this from becoming a serious problem.

These ratings relate to the feasibility of the methods of data collection of the pilot. Failure to meet success criteria, does not necessarily mean that the main evaluation should be abandoned, but will suggest that the proposed design or methods require revision. Provided the above are met or feasible alternatives can be found, we will recommend that we proceed to an efficacy trial, which will be completed via a separate ethics application. YEF will then reflect on the evidence the evaluation provides before a decision is made about the transition to the efficacy study.

The progression criteria will remain under review with more specific suggestions made as the evaluation proceeds (e.g. when it is clearer what a realistic proportion of completions of the SDQ might be possible with this cohort). Following the successful completion of this first year then we will focus on developing success criteria for the two-year efficacy study.

Methods

Study design

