The matching is done by comparing the probability that an individual is assigned to the treatment group. Therefore, a matched pair comprises two individuals with the same probability of being assigned to the treatment group, yet one of them belongs to the control group. This probability is called the propensity score. The first step of PSM is to use logistic regression to calculate the propensity scores of each individual in the sample; the second step is to match these individuals according to their propensity scores. Once a propensity score has been calculated for each observation, we will ensure that there is overlap in the range of propensity scores across treatment and comparison groups by examining the scores graphically. A second check for the quality of matching is that, the propensity scores should have a similar distribution ("be balanced") in the treated and comparison groups. We will obtain an estimate of the propensity score's distribution by splitting the sample by quintiles of the propensity score. Because the number of individuals in the control group might be different than those in the treatment group, we will use kernel-based matching. We prefer the Epanechnikov kernel with a bandwidth of 0.06, which are common choices in the literature (see, e.g., Heckman, Ichimura and Todd, 1997).

We will ensure that there is a data sharing agreement between UoB and RT and UoB and the participating NHS trusts to support these activities.

Outcomes

For contextual information, following a co-design stage working with the intervention providers, it became clear that the primary outcome should be readmission (specifically violence/abuse related) to hospital at 12 months. These data are available for both intervention and controls and we are confident that there will be sufficient power to distinguish the two groups as well providing a comparable estimate with the published literature. The key secondary outcomes will be mortality by any cause one-year post contact with RT (this will draw on NHS data captured in the Summary Hospital level Mortality Indicator and other data which captures mortality beyond 30 days post discharge). We also plan to pilot the collection of the strengths and difficulty questionnaire (SDQ) and self-report delinquency scale (SRDS). However, the latter will be piloted in the opening phases of the study, as it is not likely we will be able to collect this data on control groups.

Control quantitative data

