Our research team for this project is reasonably diverse with regards to sex, age and ethnicity. We recognise that we will be speaking to different groups of participants who are also likely to be diverse with regard to their individual characteristics and that the interaction between the researcher and participant can affect the extent and quality of data gathering. The RT intervention is not suitable for the use of peer researchers as CYP do not tend to remain in contact with the service once they have finished their work. As such we will ensure that our researchers are mindful of diversity of the groups being interviewed, and in the case of the CYP, the sensitive nature of the topics covered. However, we will not be able to offer interviewees a choice of interviewer. The training of our staff will be key to our ability to safeguard and protect CYP participating in the study.

Data collection information

Participants	Data collected	Source	Details
CYP	
 Personal identifying information Demographic information Referral information Engagement with RT SDQ/SRDS responses Reattendance at hospital data Mortality data 	
 RT RT RT RT UoB online survey platform NHS informatics team/ RT Summary Hospital level Mortality Indicator 	(*All data on CYP will be passed to YEF at which point personal details will be replaced with a Pupil Matching Reference number from the Department for Education- pseudo anonymised).
NHS / RT / Community partner organisation staff	
 Contact details/ employer name and Job role 	
 Provided by staff leads after consent given 	For researchers to arrange interview- deleted after contact made and assigned ID to reflect employer / role group.
Controls	
 Demographic information Referral information Severity and nature of injury/ level of risk to the CYP based on RT's eligibility criteria. Reattendance at hospital data Mortality data 	
 NHS informatics team 	To support propensity score matching

Outputs

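### The primary outcome is reattendance in some sections and readmission in others, and the one-year mortality clock starts at a contact that historic and uncontactable controls never had

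*Protocol*

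**What the plan says.** **Primary event.** The protocol states it in several places.

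- Mechanism for action and key outcomes: "the primary outcome should be reattendance coded for a violence or abuse related reason to hospital within 12 months from their initial discharge date".
- Outcomes (under Impact evaluation activities): "the primary outcome should be readmission (specifically violence/abuse related) to hospital at 12 months". No start date is given for the 12 months.
- Research questions and/or objectives: the overarching question is whether young people in longer-term support "have a reduced incidence of hospital re-admission for violent injury", which is narrower than violence or abuse. The primary objective is a reduction in "violence/abuse related hospital readmissions in the subsequent one-year period".
- Success criteria and/or targets, Measurement: "Hospital admission records (primary outcome"). The same section runs follow-up data collection for one year after the intervention.
- Sample size: the primary outcome is given in parentheses as re-admission.
- Data collection information: "Reattendance at hospital data" appears in both the treated and the control rows. The source is the NHS informatics team or Redthread for treated young people, and the NHS informatics team alone for controls.

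**Mortality.** "The secondary outcome will be mortality by any cause one year post contact with RT"; the Outcomes section repeats this time origin. Both sections say deaths will be drawn from the "Summary Hospital level Mortality Indicator" together with other data covering the period beyond 30 days after discharge. The data collection table names only that indicator for treated young people, and the NHS informatics team for controls.

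**Controls.** The Participants section draws them from eligible young people who did not take part, including referrals whom Redthread could not reach, or from records that predate the programme at each site. Those who refused are excluded.

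**The concern.** Reattendance and readmission are different events. The programme is based in emergency departments and most referrals come from their staff, so a return visit that ends in discharge home is entirely foreseeable. It is an event under one wording and a non-event under the other. A data request written from the measurement criterion would ask for admission records, while one written from the data table would ask for reattendances. If the event is not fixed before extraction, it can be chosen after the data have been seen.

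The clocks raise a second question. A between-group comparison needs a start date that exists in both groups. Contact with Redthread and the end of the intervention exist only for young people whom the programme reached. Where contact comes after discharge, a treated young person enters the mortality count only by having survived to that contact, and a control faces no such condition.

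**Working it through.** **1. Event, section by section**

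| Protocol section | Event | Start of the 12 months |
|---|---|---|
| Mechanism for action and key outcomes | Reattendance, violence or abuse coded | Initial discharge |
| Research question | Re-admission, violent injury | Not stated |
| Primary objective | Readmission, violence or abuse | Subsequent year, origin not stated |
| Success criteria, Measurement | Admission records | Follow-up to one year after the intervention |
| Outcomes | Readmission, violence or abuse | Not stated |
| Sample size | Re-admission | Not stated |
| Data collection table, both rows | Reattendance | Not stated |

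No section defines the terms as equivalent or says which governs.

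**2. Which start dates exist in which group**

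| Anchor | Treated | Historic controls | Referrals not reached |
|---|---|---|---|
| Initial discharge (primary outcome, one section) | Yes | Yes | Yes |
| End of intervention (follow-up period) | Yes | No | No |
| Contact with Redthread (mortality) | Yes | No | No |

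Only initial discharge is available to all. The wording on controls leaves room for other non-participants who may have had some contact, so the gap is certain for the two control types shown.

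**3. Sources**

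| Outcome | Treated row | Control row |
|---|---|---|
| Reattendance | NHS informatics team / Redthread | NHS informatics team |
| Mortality | Summary Hospital level Mortality Indicator | NHS informatics team |

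The treated mortality entry omits the additional data beyond 30 days that the text promises.

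**4. The planned sample size**

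Inputs from the Sample size section: d = 0.2, power 80%, groups of similar size. Alpha is not stated; two-sided 0.05 is assumed.

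n per group = 2 × (1.960 + 0.842)² / 0.2² = 392.4, against the stated 392. The figure reproduces. It rests on a standardised difference, so it does not change with the event chosen. What does change is the meaning of d in events prevented.

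**5. How far power depends on the event counted**

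The protocol's only illustrative rate is 7.8%, taken from a US study of repeat injury. The protocol then applies it to readmissions: 392 × 0.078 = 30.6, its 31. It gives no UK rate for either event, so the other rates below are assumptions.

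Two-proportion z-test, 392 per group, two-sided 0.05:

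power = Φ[(p₁ − p₂ − 1.96 × SE₀) / SE₁], where SE₀ uses the pooled proportion and SE₁ the separate ones.

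Worked case, p₁ = 0.078 halved to p₂ = 0.039: SE₀ = 0.01676, SE₁ = 0.01671, so (0.039 − 0.03286) / 0.01671 = 0.368 and power = 64%.

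| Control rate | Power, risk halved | Power, 30% relative reduction |
|---|---|---|
| 3% (assumed) | 29% | 12% |
| 5% (assumed) | 45% | 18% |
| 7.8% (protocol's illustration) | 64% | 26% |
| 12% (assumed) | 84% | 38% |
| 20% (assumed) | 98% | 61% |

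The table shows sensitivity to the event rate. It does not say which row belongs to reattendance and which to readmission.

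**The case against.** The other side has a good deal in its favour.

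- **The event conflict falls on both groups alike.** A reader might infer that the primary outcome cannot be measured the same way in treated and control groups. The documents do not support that: the data table asks for the same item in both rows, and one section anchors the outcome to initial discharge, which both groups have. The event is undefined, but that alone does not make it differ between groups.
- **The direction of any mortality bias is not established.** A reader might infer that the mortality comparison favours the programme. Redthread contact can occur on site before discharge, as the intervention description and the mention of an initial meeting in hospital show. It can also come later, after an off-shift referral. The order is mixed, so survival to contact is a concern only where contact follows discharge.
- **Deaths beyond 30 days are planned for.** A reader might infer from the table that treated deaths are captured for only 30 days. The text in two sections says otherwise. The table is incomplete and conflicts with that text, but it does not establish a short capture window.
- **Power need not fall.** It is tempting to treat 7.8% as the reattendance rate and scale it down for readmission. The Sample size section applies 7.8% to readmissions, so on the protocol's own use reattendance would be the more frequent event and that calculation has no basis.
- **This is a pilot.** The protocol says the first year will not support causal inference, and the efficacy study is to have its own protocol and ethics application. A violence code list may properly sit in an analysis plan.

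These points limit the claim but leave the contradictions in place. Pilot data may contribute to the final analysis, and the pilot exists to test data extraction, so the definitions matter now. These are stated rules that conflict or cannot be applied to controls, rather than detail left for later.

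**Conclusion.** The point holds in limited form. The primary event is named in two incompatible ways across at least seven places, and only one of them gives its 12-month clock a clear start. The follow-up period adds a different anchor that controls lack. The mortality year has no defined start for historic controls or for referrals who were not reached. The table's mortality source for treated young people disagrees with the text and differs from the control source; the reattendance sources also differ.

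No effect on the result can be quantified from the protocol. It supports only the statement that power for the binary outcome depends on which event is counted: 29% to 98% for a halving of risk over assumed control rates of 3% to 20%, with 392 per group, two-sided 5% and a simple two-proportion test that ignores matching. The stated 392 itself is unaffected.

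The wording should be settled before hospital data are requested.

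**What to change.** 1. Name one primary event and use it in the research question, objective, measurement criterion, Outcomes, Sample size and data collection table. Violence- or abuse-coded reattendance would match the key outcomes section and the table, with readmission as a named secondary. The essential step is a single choice made before extraction.
2. Start the 12-month clocks for the primary outcome and for mortality at the index discharge date in both groups, and restate the follow-up period on that same date instead of the end of the intervention.
3. Correct the data collection table so that deaths come from the same NHS source in both groups, covering the full year as the text intends, and reattendances likewise.

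The cost is protocol wording and one line of the data request. No new participants or data items are needed.
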